#### Statistical analysis:

The VAS, subscales and total score will be analyzed with a fixed effects model using the SAS MIXED procedure. The model will include fixed effects for treatment, region, and covariate for baseline C&A-GTS-QOL. All observed endpoint data will be used in this analysis.

Summary statistics for the VAS, subscales, and total score will be presented along with a full data listing by treatment group.

10.2.13. Mean change from Baseline (Day 1) to Week 12 in the YGTSS-TTS.

See section 10.1 for a description of the YGTSS-TTS. An exploratory analysis will be performed on the change in YGTSS-TTS from Baseline to Week 12.

#### Statistical analysis:

The mean change from Baseline (Day 1) to Week 12 (Week 4, 8 and 12 open-label) in YGTSS-TTS will be calculated. The paired t-test will be used for analyzing the change from baseline. All observed endpoint data will be used in this analysis, without imputation.

Summary statistics will be presented along with a full data listing.

10.2.14. Percentage of subjects with a decrease in their YGTSS-TTS by 25% or greater at any time point from Baseline (Day 1) to Week 12.

#### Statistical analysis:

The percent of subjects with a 25% or greater improvement on the YGTSS-TTS score at any time between the Baseline visit to the Week 12 visit (Week 4, 8 and 12) will be considered as a Response. Any subject who has at least 1 Response (>=25% improvement) will be considered as a Responder; otherwise, the subject will be considered a Non-Responder.

Summary statistics for visit week 4, week 8, week 12 and overall will be presented along with a full data listing.

In addition, the percent of subjects who have maintained Responder status from the previous visit (i.e., responder at Week 4 and still a responder at Week 8) will be presented.

Similar analyses will be performed for 50%, 75%, and 100% improvement.

10.2.15. Mean change from Baseline (Day 1) to Week 24 in the YGTSS-TTS for ecopipam compared to placebo.

See section 10.1 for a description of the YGTSS-TTS. An exploratory analysis will be performed on the change in YGTSS-TTS from Baseline to Week 24 (Weeks 4, 8, 12, 13, 14, 15, 16, 18, 20, 22 and 24).

### Statistical analysis:

The analysis method for the YGTSS-TTS will be analyzed with a Mixed Model for Repeated Measures (MMRM) model using the SAS MIXED procedure with REPEATED statement. The model with an unstructured covariance matrix will include fixed effects for treatment, visit, interaction between treatment and visit, region, age group (0 = children 6-11, 1 = adolescents 12-17, 2=adults >=18) and covariate for baseline YGTSS-TTS. Visit will include weeks 4, 8, 12, 13,14,15,16,18,20, 22 and 24. By visit comparisons will be provided. In the event the model does not converge using the unstructured covariance matrix, the methods described in Section 10.2.4 will be tried. The final covariance structure will be documented in the table. All observed endpoint data will be used in this analysis, without imputation.

Summary statistics will be presented along with a full data listing by treatment group.

10.2.16. Mean change from Baseline (Day 1) to Week 24 in the YGTSS-GS for ecopipam compared to placebo.

See section 10.1 for a description of the YGTSS-GS. An exploratory analysis will be performed on the change in YGTSS-TTS from Baseline to Week 24 (Weeks 4, 8, 12, 13, 14, 15, 16, 18, 20, 22 and 24).

#### Statistical analysis:

The analysis method for the YGTSS-GS score will be analyzed with a Mixed Model for Repeated Measures (MMRM) model using the SAS MIXED procedure with REPEATED statement. The model with an unstructured covariance matrix will include fixed effects for treatment, visit, interaction between treatment and visit, region, age group (0 = children 6-11, 1 = adolescents 12-17, 2=adults >=18) and covariate for baseline YGTSS-GS. Visit will include weeks 4, 8, 12, 13,14,15,16,18,20, 22 and 24. By visit comparisons will be provided. In the event the model does not converge using the unstructured covariance matrix, the methods described in Section 10.2.4 will be tried. The final covariance structure will be documented in the table. All observed endpoint data will be used in this analysis, without imputation.

Summary statistics will be presented along with a full data listing by treatment group.

10.2.17. Mean change from Baseline (Day 1) to Week 24 in the Clinical Global Impression of Tourette Syndrome Severity (CGI-TS-S) for ecopipam compared to placebo.

See section 10.2.2 for a description of the CGI-TS-S. An exploratory analysis will be performed on the change in CGI-TS-S score from Baseline to Week 24 (Weeks 4, 8, 12, 13, 14, 15, 16, 18, 20, 22 and 24)

Statistical analysis:

This document is confidential.

SAP text Version: SAP text 3.0 6-Dec-2023

Controlled Document ID: 3903A.02, Effective Date 31-Aug-2020

The analysis method for the CGI-TS-S score will be analyzed with a Mixed Model for Repeated Measures (MMRM) model using the SAS MIXED procedure with REPEATED statement. The model with an unstructured covariance matrix will include fixed effects for treatment, visit, interaction between treatment and visit, region, age group (0 = children 6-11, 1 = adolescents 12-17, 2=adults >=18) and covariate for baseline CGI-TS-S. Visit will include weeks 4, 8, 12, 13,14,15,16,18,20, 22 and 24. By visit comparisons will be provided. In the event the model does not converge using the unstructured covariance matrix, the methods described in Section 10.2.4 will be tried. The final covariance structure will be documented in the table. All observed endpoint data will be used in this analysis, without imputation.

Summary statistics will be presented along with a full data listing by treatment group.

10.2.18. Caregiver Global Impression of Change (CaGI-C) through Week 24 for ecopipam compared to placebo.

See section 10.2.7 for a description of the CaGI-C. An exploratory analysis will be performed on the CaGI-C through Week 24 (Weeks 4, 12, 18 and 24).

#### Derived Variables and Statistical analysis:

CaGI-C rating will be categorized as Improved (1 (very much improved), 2 (much improved), 3 (minimally improved), No change and Worsened (5 (minimally worse, 6 (much worse), and 7 (very much worse)). All observed endpoint data will be used in this analysis, without imputation. Chi-Square test will be used to compare between treatment group.

Summary statistics will be presented along with a full data listing by treatment group.

10.2.19. Mean change from Randomization (Week 12) to Week 24 in the Change in Gilles de la Tourette Syndrome—Quality of Life Scale for Children and Adolescents (C&A-GTS-QOL) for ecopipam compared to placebo.

See section 10.2.11 for a description of the C&A-GTS-QOL. An exploratory analysis will be performed on the change in C&A-GTS-QOL score from Week 12 to Week 24.

#### Statistical analysis:

The analysis method for the C&A-GTS-QOL score will be analyzed with a fixed effects model using the SAS Mixed procedure. The model will include fixed effects for treatment, region, age group (0 = children 6-11, 1 = adolescents 12-17) and covariate for week 12 C&A-GTS-QOL. All observed endpoint data will be used in this analysis, without imputation.

Summary statistics for the VAS, subscales, and total score will be presented along with a full data listing by treatment group.

10.2.20. Clinical Global Impression of Tourette Syndrome Improvement (CGI-TS-I) through Week 24 for ecopipam compared to placebo.

See section 10.2.2 for a description of the CGI-TS-I. An exploratory analysis will be performed on the change in CGI-TS-I score through Week 24 (Weeks 4,12,13, 14, 15, 16, 18, 20, 22 and 24).

#### Derived Variables and Statistical analysis:

CGI-TS-I rating will be categorized as Improved (1 (very much improved), 2 (much improved), 3 (minimally improved), No change and Worsened (5 (minimally worse, 6 (much worse), and 7 (very much worse)). All observed endpoint data will be used in this analysis, without imputation. Chi-Square test will be used to compare between treatment group.

Summary statistics will be presented along with a full data listing by treatment group.

10.2.21. Time from Randomization (Week 12) to treatment discontinuation during the double-blind R/WD period for ecopipam compared to placebo.

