- Mean change from Baseline (Day 1) to Week 24 in the YGTSS-TTS for ecopipam compared to placebo.
- Mean change from Baseline (Day 1) to Week 24 in the YGTSS-GS score for ecopipam compared to placebo.
- Mean change from Baseline (Day 1) to Week 24 in the Clinical Global Impression of Tourette Syndrome Severity (CGI-TS-S) for ecopipam compared to placebo.

- Caregiver Global Impression of Change (CaGI-C) through Week 24 for ecopipam compared to placebo.
- Mean change from Randomization (Week 12) to Week 24 in Gilles de la Tourette Syndrome—Quality of Life Scale for Children and Adolescents (C&A-GTS-QOL) for ecopipam compared to placebo.
- Mean change from Baseline (Day 1) to Week 24 in the Clinical Global Impression of Tourette Syndrome Improvement (CGI-TS-I) for ecopipam compared to placebo.
- Time from Randomization (Week 12) to treatment discontinuation during the double-blind R/WD period for ecopipam compared to placebo.
- Time from Randomization (Week 12) to loss of ≥ 100% of the improvement experienced on the Yale Global Tic Severity Scale- Total Tic Score (YGTSS-TTS) from Baseline (Day 1) to the last visit (Week 12) in the open-label Stabilization period for ecopipam compared to placebo.
- To evaluate the population PK/pharmacodynamic (PD) relationships with ecopipam during the open-label Stabilization period of the study.

Additional analyses will include efficacy endpoints listed above at all earlier timepoints and the YGTSS subscales individually (Motor, Vocal, and Impairment). The correlation between subjects meeting Relapse criteria based on YGTSS-TTS and those who also had at least a 1-point reduction on CGI-TS-S will also be investigated. If there is a strong correlation between subjects ≥6 and <18 years who meet Relapse criteria based on the YGTSS-TTS and have a worsening by at least one category of the CGI-TS-S, Relapse will not be a competing risk, and therefore the time to worsening of the CGI-TS-S for subjects ≥6 and <18 years will be considered a secondary endpoint. Similarly, if there is a strong correlation between all subjects irrespective of age who meet Relapse criteria based on the YGTSS-TTS and have a worsening by at least one category of the CGI-TS-S, Relapse will not be a competing risk, and therefore the time to worsening of the CGI-TS-S for all subjects irrespective of age will be considered a secondary endpoint.

Subgroup analyses will also be conducted on all efficacy endpoints listed above for the following populations:

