13.4. Planned Analysis

13.4.1. Efficacy Analysis

The primary efficacy endpoint is time from Randomization to Relapse defined as a loss of $\geq 50\%$ of the improvement experienced on the YGTSS-TTS at the last visit in the open-label Stabilization period (Week 12), or initiation of additional medications to treat symptoms of TD, or requirement of hospitalization for w rsening symptoms of TD in subjects ≥ 6 and < 18 years during the double-blind R/WD period for ecopipam compared to placebo. Data from subjects who complete or discontinue from the double-blind R/WD period without Relapse will be considered as censored obs rvations. The log rank test will be the primary test of statistical significance. Kaplan-Meier curves will be used to compare the times to relapse between the treatment groups. The hazard ratio and its 95% confidence interval (CI) will be estimated from the Cox proportional hazard model with treatment as a factor. The proportional hazards assumption will be evaluated graphically and analytically, for example by assessing martingale and Schoenfeld residuals and by modeling time-dependent covariates. The analysis of the primary efficacy endpoint will be performed in the mITT and PP populations according to the randomized treatment. Details will be provided in the Statistical Analysis Plan.

The time-to-event secondary and exploratory endpoints related to Relapse will be analyzed in a similar manner as the primary endpoint. The exploratory endpoints of mean change will be assessed with a Mixed Model for Repeated Measures (MMRM) model using the SAS MIXED procedure, with a REPEATED statement, with no imputation. The model will include fixed effects for treatment, visit, the interaction between treatment and visit, and a covariate for baseline score for the given assessment and other covariates such as gender, age group, race/ethnicity, and region. All secondary and exploratory endpoints will be analyzed in the mITT population according to randomized treatment. Details will be provided in the Statistical Analysis Plan.

Protocol EBS-101-TD-301 Version 9.0, 05 March 2024

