# 14. Changes from Analysis Planned in Protocol

There are no changes from the analysis planned in protocol.

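### The three-category chi-square for CaGI-C and CGI-TS-I through Week 24 discards ordering and shifts within ratings 1-3, and the SAP does not declare its change to the protocol's CGI-TS-I endpoint

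*SAP*

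**What the plan says.** SAP 10.2.20 defines the CGI-TS-I analysis through Week 24 by collapsing the rating: "CGI-TS-I rating will be categorized as Improved (1 (very much improved), 2 (much improved), 3 (minimally improved), No change and Worsened", where Worsened covers ratings 5 to 7. The comparison is one sentence: "Chi-Square test will be used to compare between treatment group". SAP 10.2.18 does the same for the caregiver rating: "CaGI-C rating will be categorized as Improved (1 (very much improved), 2 (much improved), 3 (minimally improved), No change and Worsened". Neither section gives an effect estimate, covariates or strata, or says how order is used.

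The protocol treats the two ratings differently. Section 11.3 lists CGI-TS-I as "Mean change from Baseline (Day 1) to Week 24 in the Clinical Global Impression of Tourette Syndrome Improvement (CGI-TS-I) for ecopipam compared to placebo", and section 13.4.1 says "The exploratory endpoints of mean change will be assessed with a Mixed Model for Repeated Measures (MMRM) model using the SAS MIXED procedure". For the caregiver rating, section 11.3 lists only "Caregiver Global Impression of Change (CaGI-C) through Week 24 for ecopipam compared to placebo", with no mean change. SAP 5.3 rewords the CGI-TS-I endpoint as the rating through Week 24 (endpoint 19). SAP 14 states "There are no changes from the analysis planned in protocol".

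The SAP also keeps a full-scale MMRM of change from Week 12 to Week 24 for both ratings: 10.2.7 for CaGI-C and 10.2.9 for CGI-TS-I.

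**The concern.** Both instruments are ordered seven-level ratings (CaGI-C adds a code 0 for not rated). Merging 1, 2 and 3 into one cell removes the distinction between very much, much and minimally improved. Only subjects with at least 25% YGTSS-TTS improvement at both Week 8 and Week 12 are randomized, and both ratings refer back to the start of the study, so many subjects in both arms may sit in that merged cell. A plausible pattern is that ecopipam subjects stay at 1-2 while placebo subjects drift to 3. The three-category table would not register that drift, although SAP 10.2.2 itself defines a CGI-TS-I of 1 or 2 as positive response. A Pearson chi-square on the remaining three cells also ignores their order.

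Two things are at stake. The p-values for endpoints 17 and 19 could be insensitive and could disagree with the MMRM results on the same ratings. And a reader comparing protocol and SAP finds a changed CGI-TS-I endpoint that SAP 14 does not mention.

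**Working it through.** **The plan's own figure.** The documents give no power for either rating. The only stated power is 85% for the primary endpoint, and it reproduces with Freedman's formula: ((1+0.4)/(1-0.4))² × (1.960+1.036)² = 5.444 × 8.978 = 48.9, so 49 events. With 49 children and adolescents per arm, 49×0.65 + 49×0.34 = 48.5 events.

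**Sample sizes.**
- CaGI-C is given only to ages 6-17: 49 per arm.
- CGI-TS-I covers all ages. Of about 40 adults, about 20 would be randomized if the 50% response rate also applies to them (an assumption): (98+20)/2 = 59 per arm.
- If relapsers drop out of the Week 24 comparison: 59×(1-0.65) ≈ 21 placebo and 59×(1-0.34) ≈ 39 ecopipam.

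**Effect and spread, from Protocol Table 2 (n = 74 and 75).** SD = difference / z(p) / √(1/74+1/75), with √(1/74+1/75) = 0.1639.
- CGI-TS-I, 3.42 vs 3.04, p = 0.079: 0.38/1.757/0.1639 = 1.32.
- CaGI-C, 3.55 vs 2.49, p = 0.007: 1.06/2.697/0.1639 = 2.40.

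**Model.** A normal variable is cut at 1.5, 2.5, …, 6.5 to give ratings 1-7. One visit, two-sided 5%. Pearson chi-square on {1-3}, {4}, {5-7} is compared with the Wilcoxon test on 1-7. Under the null both hold about 5%.

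For CGI-TS-I the chi-square sees these cells. Ecopipam: Φ((3.5-3.04)/1.32) = 64% improved, 23% unchanged, 13% worsened. Placebo: Φ((3.5-3.42)/1.32) = 52%, 27%, 21%.

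| Scenario | n (placebo/ecopipam) | Chi-square | Wilcoxon |
|---|---|---|---|
| CGI-TS-I, Phase 2b means, SD 1.32 | 59/59 | 19-20% | 30-32% |
| CGI-TS-I, same inputs | 49/49 | 17% | 27% |
| CGI-TS-I, same inputs | 21/39 | 13% | 17% |
| CaGI-C, Phase 2b means, SD 2.40 | 49/49 | 36% | 54% |
| CaGI-C, Phase 2b means, SD 1.32 (CGI-TS-I value) | 49/49 | 82% | 96% |
| CGI-TS-I, mixture of relapsers and non-relapsers at 65%/34% | 59/59 | 13-28% | 31-51% |
| CGI-TS-I, non-relapsers only, same distribution in both arms | 21/39 | about 4% | about 5% |

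The mixture row assumes relapsers centre on 3.0-3.5 and non-relapsers on 2.0-2.2, with SD 0.9-1.0. Over a wider assumed grid (ecopipam mean 2.0-3.5, SD 1.0-1.6, several effect sizes, 49 or 59 per arm), the loss ran from about 7 to 50 points. It was smallest when the rank test already had very high power and largest when most subjects in both arms rated 1-3.

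**Protocol against SAP, CGI-TS-I.** The protocol endpoint is a change from Baseline, to be fitted with a baseline-score covariate. Protocol 11.3.1 says the improvement rating already compares the subject with Baseline, and the schedule of assessments in both documents has no CGI-TS-I at Baseline (SAP 10.2.2 lists one, contrary to that schedule). The change from Baseline therefore cannot be formed as written.

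**The case against.** The strongest reply is that the same ratings already have a full-scale analysis. SAP 10.2.7 and 10.2.9 fit MMRMs adjusted for the Week 12 rating, region and age group, and the proposed ordinal comparison asks nearly the same question. Endpoints 17 and 19 are exploratory and outside the fixed testing sequence in SAP 10.2, so no confirmatory conclusion depends on them. A proportion-improved table beside an MMRM is a legitimate complement. All of this stands, and it limits the point to a cheap improvement.

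The power figures are also soft. Table 2 comes from an MMRM with imputation, so an SD back-calculated from its p-values is rough. Cutting the CaGI-C normals to 1-7 with SD 2.40 gives means of about 2.8 and 3.6, a difference of about 0.8 rather than 1.06. Phase 2b patients were not selected responders, and the mixture means are assumed. Which subjects count at Week 24 is itself unsettled: SAP 8.4 moves early-termination data to the next scheduled visit, while SAP 8.1 summarizes by nominal visit. This stands too.

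Finally, the SAP names neither Pearson nor an unordered test. A Mantel-Haenszel chi-square is not excluded and would recover part of the loss: 24.8% for CGI-TS-I at 59 per arm, against 19.5% for Pearson and 31.2% for Wilcoxon. It would still merge ratings 1-3.

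A reader might infer more: that a real effect on these ratings would go undetected, or that the SAP discarded a workable protocol model. The documents support neither. The Week 12 to Week 24 MMRMs remain, and the protocol's model needs a Baseline rating that is not scheduled. Nor is there a protocol departure for CaGI-C, because the protocol names no mean change for that endpoint.

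**Conclusion.** The point holds as a modest one. For endpoints 17 and 19, the three-category chi-square is less sensitive than a test that uses all seven levels. With Phase 2b means and all randomized subjects contributing at a visit, the loss is about 10 to 20 points of power. That range is a simulation result, not a figure from the documents, and should not be read as fixed. It falls to about 4 points with 21 against 39 subjects, and to nothing if the remaining non-relapsers have the same distribution in both arms. It can exceed 20 points if most subjects in both arms rate 1-3. The primary and secondary endpoints and the Week 12 to Week 24 analyses are unaffected.

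Separately, and without any simulation, SAP 14 is inaccurate for CGI-TS-I: the protocol's mean-change endpoint was replaced and the change was not declared. Replacing it was reasonable, since it cannot be computed as written; what is missing is the record.

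**What to change.** - In SAP 10.2.18 and 10.2.20, compare the observed 1-7 rating between arms at each post-randomization visit (Weeks 18 and 24 for CaGI-C; Weeks 13 to 24 for CGI-TS-I) with an ordinal method. Either use a van Elteren test stratified by region and age group, or a proportional-odds model with treatment, region, age group and the Week 12 rating, reporting the common odds ratio and its 95% CI.
- Set CaGI-C code 0 (not rated) to missing; the present categories give it no place.
- Keep the three-category table as a descriptive display.
- In SAP 14, record that the protocol's CGI-TS-I mean-change endpoint is analysed as the observed rating, because no Baseline rating is scheduled and the rating is already relative to Baseline. Correct the Baseline entry for CGI-TS-I in SAP 10.2.2 to match the schedule.

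The cost is SAP wording and minor reprogramming for two exploratory endpoints, with no new data or subjects. The one statistical downside is the common-odds-ratio assumption if proportional odds is chosen; the van Elteren test avoids it.

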#### Statistical analysis:

An exploratory analysis will be performed on all randomized subjects in R/WD period to find time from randomization to study or treatment discontinuation. The analysis method will be similar to the primary efficacy analysis as described in Section 10.1. Data from subjects who complete the study will be considered as censored observations. The log rank test will be the primary test of statistical significance. Kaplan-Meier curves will be used to compare the times to treatment discontinuation between the treatment groups. The hazard ratio and its 95% confidence interval (CI) will be estimated from the Cox proportional hazard model with treatment as a factor. All observed endpoint data will be used in this analysis, without imputation.

10.2.22. Time from Randomization (Week 12) to loss of ≥ 100% of the improvement experienced on the YGTSS-TTS from Baseline (Day 1) to the last visit (Week 12) in the open-label Stabilization period for ecopipam compared to placebo.

#### Statistical analysis:

An exploratory analysis will be performed on all randomized subjects in R/WD period. The analysis method will be similar to the primary efficacy analysis as described in Section 10.1. Data from subjects who complete or discontinue from the double-blind R/WD period without loss of  $\geq$  100% of the improvement will be considered as censored observations. The log rank test will be the primary test of statistical significance. Kaplan-Meier curves will be used to compare the times to loss of  $\geq$  100% of the improvement between the treatment groups. The hazard ratio and its 95% confidence interval (CI) will be estimated from the Cox proportional hazard model with treatment as a factor. All observed endpoint data will be used in this analysis, without imputation.

This document is confidential.

SAP text Version: SAP text 3.0 6-Dec-2023

Controlled Document ID: 3903A.02, Effective Date 31-Aug-2020

10.2.23. Mean change from Randomization (Week 12) to Week 24 in the YGTSS subscales (Motor, Vocal, and Impairment) for ecopipam compared to placebo.

An exploratory analysis will be performed on the change in each of the YGTSS subscales from randomization to Week 24.

